9.4 Analysis of the primary variable(s)

9.4.1 Variables

The primary efficacy variable is the time-averaged proportional change from baseline in NT-proBNP. Weeks 4 and 8 will be included in the analysis (primary analysis time point).

9.4.2 Statistical model, hypothesis, and method of analysis

The primary hypothesis to be tested is that the ratio of the geometric means of NT -proBNP (average of Weeks 4 and 8/baseline) for the sacubitril/valsartan and enalapril groups are equal (H0) versus the ratio of the geometric means of NT-proBNP are not equal (Ha).

For NT-proBNP, the time-averaged proportional change from baseline in a logarithmic scale will be analyzed using an analysis of covariance (ANCOVA) model using data from Weeks 4 and 8 with treatment as a fixed effect factor and the logarithmic baseline biomarker value as a covariate The estimated treatment effect in terms of ratios of geometric means, based on the least-squared means from the ANCOVA model, and the corresponding two -sided 95% confidence intervals will be provided. Baseline is Week 0.

The change from baseline log-transformed NT-proBNP will be calculated as log (post-dose value) – log (baseline value). Geometric means (presented as a ratio to baseline) will be calculated by exponentially back-transforming the LS means based on the ANCOVA model.

9.4.3 Handling of missing values/censoring/discontinuations

The analysis will be performed based on all available data in the FAS and based on likelihood method with an assumption of missing at random for missing data.

9.4.4 Supportive analyses

T-tests comparing treatment groups using change from log (baseline) to log (Week 8) values and log (Week 4) values will be performed.

In addition to the primary analysis, the primary efficacy variable will also be analyzed using the same analysis model in the PP Set as supportive.

9.5 Analysis of secondary and exploratory variables

9.5.1 Secondary variables

For NT-proBNP at Week 8, a proportional change from baseline in a logarithmic scale will be analyzed using an ANCOVA model with treatment as a fixed effect factor and the logarithmic baseline biomarker value as a covariate. The estimated treatment effects in terms of ratios of geometric means, based on the least-squared means from the ANCOVA model, and the corresponding two-sided 95% confidence intervals will be provided. Baseline is Week 0. Week 4 will be used if the Week 8 value is missing.

Incidences of symptomatic hypotension, hyperkalemia and angioedema will be calculated, along with the relative risk of sacubitril/valsartan vs. enalapril and 95% confidence intervals of the relative risk.

For biomarkers including BNP to NT-proBNP ratio, hs-Troponin, and urinary cGMP, the time-averaged proportional change from baseline in a logarithmic scale will be analyzed using an ANCOVA model using the data from Weeks 4 and 8 with treatment as a fixed effect factor and the logarithmic baseline biomarker value as a covariate. The estimated treatment effects in terms of ratios of geometric means, based on the least-squared means from the ANCOVA model, and the corresponding two-sided 95% confidence intervals will be provided. Baseline is Week 0.

For BNP to NT-proBNP ratio and urinary cGMP at Weeks 1 and 2, a proportional change from baseline in a logarithmic scale will be analyzed using an ANCOVA model with treatment as a fixed effect factor and the logarithmic baseline biomarker value as a covariate. For each of Weeks 1 and 2 the estimated treatment effects in terms of ratios of geometric means, based on the least-squared means from the ANCOVA model, and the corresponding two-sided 95% confidence intervals will be provided. Baseline is Week 0.

Analyses of the secondary variables will be based on the FAS.

ſ

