5.3 Treatment assignment, randomization

The randomization numbers will be generated using the following procedure to ensure that treatment assignment is unbiased and concealed from patients and investigator staff. A randomization list will be produced by or under the responsibility of Novartis D rug Supply

Management using a validated system that automates the random assignment of treatment arms to randomization numbers in the specified ratio.

Confidential

Eligible patients will be randomized no earlier than 24 hours after presentation at the hospital and no later than within ten days of admission, while still hospitalized, via IWRS to one of the treatment arms. The investigator or his/her delegate will contact the IWRS after confirming that the patient fulfills all the study entry criteria. The IWRS will assign a randomization number to the patient, which will be used to link the patient to a treatment arm and will specify which bottle from the centralized hospital supply the patient will be dosed for the first day and a unique medication number for the first package of investigational treatment to be dispensed to the patient. The initial dose will be determined by the patient's blood pressure at the time of the call to the IWRS.

The randomization numbers will be generated using the following procedure to ensu re that treatment assignment is unbiased and concealed from patients and investigator staff. A patient randomization list will be produced by the IWRS provider using a validated system that automates the random assignment of patient numbers to randomization numbers. These randomization numbers are linked to the different treatment arms, which in turn are linked to medication numbers. A separate medication list will be produced by or under the responsibility of Novartis Drug Supply Management using a validat ed system that automates the random assignment of medication numbers to packs containing the investigational drug(s).

Initial dose at randomization will be determined by systolic blood pressure (SBP). See Table 5-3.

Dose adjustments to lower dose levels may be made at any time at both scheduled and unscheduled visit only if clinically indicated for blood pressure control/tolerability reasons. Dose adjustments to increase dose levels may be made at any time at both scheduled and unscheduled visits based on clinical need or investigator judgement.

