8.5 Adjudication Committee

It is important that the investigator pays special attention to any swelling or edema that may resemble angioedema or angioedema-like events that may be reported by patients. There will be a separate eCRF for angioedema events. If such an event occurs, the investigator will complete an Adjudication Questionnaire for an Angioedema-like Event form (provided by Novartis) to summarize the event, its treatment, and its ultimate outcome and communicate this report to Novartis as soon as possible. Follow-up reports must be communicated to Novartis as soon as new information regarding the event becomes available. All hospital records related to the event must be communicated to Novartis.

Occasionally, the investigator may be contacted by the Novartis regarding AEs that were reported on behalf of patients that may resemble an angioedema -like event. The investigator or his/her delegated staff must complete the required report forms and supply the required medical records for such events, regardless of whether the investigator views the event in question as angioedema or not.

All angioedema reports will be forwarded to an angioedema adjudication committee by Novartis for assessment.

Submission of an angioedema report is not a substitution for the submission of a SA E report. If an angioedema-like event satisfies the definition of a SAE, the investigator must submit a SAE report in addition to the Adjudication Questionnaire for an Angioedema-like Event.

9 Data analysis

A designated Contract Research Organization will perform the statistical analysis.

It is planned that the data from all centers that participate in this protocol will be combined, so that an adequate number of subjects will be available for analysis.

Unless otherwise specified, all statistical tests will be conducted against a two-sided alternative hypothesis, employing a significance level of 0.05.

Efficacy, safety, and other data will be summarized. For continuous variables, summary statistics (mean, standard deviation, median, 25th and 75th percentiles, interquartile range, minimum, and maximum) at each time point and for change from baseline to each time point will be reported by treatment group.

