9.7 Sample size calculation

Assuming a significance level of 0.05 and 85% power, a sample size of 882 patients would be needed to detect an 18% reduction in the geometric mean of the time-averaged proportional change from baseline (average of Weeks 4 and 8) in NT-proBNP for the sacubitril/valsartan treatment group assuming a value of 0.95 for the enalapril group, a common standard deviation of 0.85 and a 25% rate of missing/non-evaluable samples. The estimates are based on the day 5 to day 14 data from the RELAX -AHF study. The standard deviation estimate is supported by data from PARADIGM.

The assumption of a 18% reduction in the geometric mean for NT-proBNP for the sacubitril/valsartan treatment group vs. the enalapril group is consistent with NT-proBNP results seen in PARADIGM (26% and 25% relative reduction of sacubitril/valsartan vs. enalapril at Week 4 and Month 8 respectively), PARAMOUNT (23% relative of sacubitril/valsartan vs. valsartan at Week 12) and RELAX-AHF (19% relative reduction of serelaxin vs. placebo at Day 2).

		0	10 1			
Change in GM for enalapril	Common SD	Relative reduction in GM for sacubitril/valsartan group compared to enalapril group	Change in GM for sacubitril/valsartan group	Power	Non- evaluable rate	Total sample size after adjusting for non- evaluable rate
.95	.85	15%	.81	85%	10%	1096
.95	.85	15%	.81	90%	10%	1280
.95	.85	18%	.78	85%	10%	736
.95	.85	18%	.78	90%	10%	860
.95	.85	18%	.78	85%	25%	882
.95	.85	20%	.76	85%	10%	582
.95	.85	20%	.76	90%	10%	680

Table 9-1Sample size and power for various rate of reduction in
sacubitril/valsartan group given alpha =0.05:

10 Ethical considerations

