1.1 Study design

This study will use a randomized, double-blind, double-dummy, active-controlled, parallel group design. Eligible patients hospitalized for acute decompensated heart failure (ADHF) will be randomized no earlier than 24 hours and up to ten days of presentation while still hospitalized. A total of approximately 882 patients randomized to sacubitril/valsartan or enalapril in a 1:1 ratio is planned with no stratification.

At the time of randomization, patients will have been stabilized, defined for this study as:

- Systolic blood pressure (SBP) \geq 100 mmHg for the preceding 6 hours prior to randomization; no symptomatic hypotension
- No increase (intensification) in intravenous (i.v.) diuretic dose within last 6 hours prior to randomization
- No i.v. inotropic drugs for 24 hours prior to randomization
- No i.v. vasodilators including nitrates within last 6 hours prior to randomization

All patients will need to meet all other inclusion and none of the exclusion criteria.

In order to provide for a necessary 36 hour washout of prior angiotensin converting enzyme inhibitors (ACEi) treatment prior to receiving sacubitril/valsartan (known as LCZ696 in prior trials), the supplied blinded study drug for those allocated to sacubitril/valsartan will be placebo only until the 3rd dose. Because the study is blinded, all patients, regardless of randomization arm, need to remain in the hospital for six hours after they have received their 3rd dose of study medication.

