2.7.2 Statistical hypothesis, model, and method of analysis

For NT-proBNP at Week 8, a proportional change from baseline in a logarithmic scale will be analyzed using an ANCOVA model with treatment as a fixed effect factor and the logarithmic baseline biomarker as a covariate. The estimated treatment effects in terms of ratios of geometric means, based on the LS means from the ANCOVA model, and the corresponding two-sided 95% confidence intervals will be provided. Baseline is Week 0. Week 4 will be used if the Week 8 value is missing.

The incidence of symptomatic hypotension up to Week 8 will be calculated by treatment group. The relative risk (sacubitril/valsartan vs. enalapril) and the 95% confidence interval will also be presented. Similarly, the incidence of hyperkalemia, all angioedema, and positively adjudicated angioedema during the 8 week double-blind phase and the relative risk (sacubitril/valsartan vs. enalapril) will be summarized. Additionally, medication change, lowest documented systolic blood pressure and lowest documented diastolic blood pressure will be summarized by treatment group for symptomatic hypotension. The highest potassium value documented for hyperkalemia will also be summarized by treatment group.

For biomarkers including BNP, BNP to NT-proBNP ratio, NT-proBNP to BNP ratio, hs-Troponin T, UcGMP, and UcGMP to urinary creatinine ratio, the time-averaged proportional change from baseline in a logarithmic scale will be analyzed using an ANCOVA model using data from Weeks 4 and 8 with treatment group as a fixed effect factor and the logarithmic baseline biomarker value as a covariate.

Similar to the primary endpoint, the values from Weeks 4 and 8 will be averaged and the change from baseline will be calculated.

The estimated treatment effect in terms of ratios of geometric means, based on the LS means from the model, and the corresponding two-sided 95% confidence intervals will be presented. The geometric means (presented as a ratio to baseline) will be calculated by exponentially back transforming the LS means based on the ANCOVA model.

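### The relative risks of symptomatic hypotension and hyperkalemia leave out baseline systolic pressure and potassium: valid, but slightly less precise than the collected data allow

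*Protocol*

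**What the plan says.** Symptomatic hypotension, hyperkalemia and angioedema over 8 weeks are three of the five secondary objectives (Protocol 2.2, SAP 1.2). Protocol 9.5.1 gives their whole analysis in one sentence: "Incidences of symptomatic hypotension, hyperkalemia and angioedema will be calculated, along with the relative risk of sacubitril/valsartan vs. enalapril and 95% confidence intervals". SAP 2.7.2 says for symptomatic hypotension: "The relative risk (sacubitril/valsartan vs. enalapril) and the 95% confidence interval will also be presented". It then says that hyperkalemia and angioedema are handled similarly. No regression model, stratification or covariate is named for any of the three.

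In the same two sections, each biomarker endpoint is analyzed by ANCOVA with its own log baseline as covariate.

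The design does not balance these baselines either. SAP 1.1 describes the allocation as "1:1 ratio is planned with no stratification". Yet both values are on file. Blood pressure is taken at every visit (Protocol 6.5.2), and potassium is measured at Visit 1 for eligibility and at Visit 2 by the central laboratory (Protocol 6.5.5.2).

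The documents treat both as relevant to risk. On SBP, Protocol 5.3 says: "Initial dose at randomization will be determined by systolic blood pressure (SBP". SAP 2.2.1 makes SBP at randomization and baseline eGFR subgroups for the adverse events of special interest. Potassium has an eligibility ceiling (Protocol 4.2) but no subgroup.

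**The concern.** Pressure at entry is a natural predictor of later symptomatic hypotension, and potassium and eGFR at entry of later hyperkalemia. If they predict well, a relative risk that leaves them out has a wider interval than it needs. Any difference between the arms in these baselines that arises by chance also stays in the point estimate. Safety and tolerability of in-hospital initiation is in the trial's title, so readers will look closely at these two intervals. The plan already accepts baseline adjustment for the biomarkers and applies none here. An adjusted estimate added after unblinding, because an imbalance had been seen, would look data-driven. The question is how much precision is at stake.

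**Working it through.** **The plan's own figure.** The only sizing is for NT-proBNP: "Assuming a significance level of 0.05 and 85% power, a sample size of 882 patients would be needed to detect an 18% reduction", with "a common standard deviation of 0.85 and a 25% rate of missing/non-evaluable samples", and the opening of Protocol section 9 makes tests two-sided. Per arm, 2(1.960 + 1.036)² × 0.85² / (ln 0.82)² = 329.4, so 330; 660 in total; 660 / 0.75 = 880, against 882 stated. The figure reproduces to within 2 patients. At 1:1 it gives 441 per arm. The documents give no precision target for the safety relative risks.

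**Inputs.** n = 441 per arm. Event rates are from Protocol 1.1: Table 1-1 (hypotension 18% vs 12%, hyperkalemia 12% vs 14%) and the titration study (hypotension 9.7% and 8.4%, hyperkalemia 7.7% and 4.4%). They are illustrative only. Both sources are in chronic heart failure with different follow-up, Table 1-1 reports hypotension rather than symptomatic hypotension, and the titration study compares two sacubitril/valsartan regimens. Prognostic strength is an assumption: an odds ratio (OR) per SD of one normally distributed baseline value, from 1.25 to 2.7.

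**Crude interval.** Var(log RR) = (1 − p₁)/(n p₁) + (1 − p₀)/(n p₀). For 18% vs 12%: 0.82/(441 × 0.18) + 0.88/(441 × 0.12) = 0.01033 + 0.01663 = 0.02696. The SE is 0.1642, and the RR is 1.50 (95% CI 1.09 to 2.07).

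**Adjusted interval.** Let m₁(x) and m₀(x) be the logistic risks at baseline x, with means p₁ and p₀. The large-sample variance of the standardized log RR is E[m₁(1 − m₁)]/(n p₁²) + E[m₀(1 − m₀)]/(n p₀²) + Var(m₁/p₁ − m₀/p₀)/(2n). For 18% vs 12% at OR 2.0 the two expectations are 0.1378 and 0.1002. The sum is 0.00964 + 0.01578 + 0.00001 = 0.02543, so the SE is 0.1595. The log-scale interval narrows by 1 − 0.1595/0.1642 = 2.9%, and the 95% CI becomes 1.10 to 2.05.

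**Narrowing of the log-scale 95% CI, all four rate pairs:**

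| Rates | Crude RR (95% CI) | OR 1.25 | OR 1.5 | OR 2.0 | OR 2.7 |
|---|---|---|---|---|---|
| Hypotension 18% vs 12% | 1.50 (1.09-2.07) | 0.3% | 1.0% | 2.9% | 5.7% |
| Hyperkalemia 12% vs 14% | 0.86 (0.61-1.21) | 0.3% | 0.9% | 2.7% | 5.4% |
| Hypotension 9.7% vs 8.4% | 1.15 (0.76-1.76) | 0.2% | 0.7% | 2.1% | 4.3% |
| Hyperkalemia 7.7% vs 4.4% | 1.75 (1.02-3.01) | 0.1% | 0.45% | 1.4% | 3.1% |

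Variance falls by about twice these percentages (5.7% in the worked example).

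**Chance imbalance.** The SD of the difference in baseline means is √(2/441) = 0.067 SD, and the 95% limit is 1.96 × 0.067 = 0.13 SD. The log RR moves by the imbalance times the average slope of log risk. For 18% vs 12% at OR 2.0 the slope is ln 2 × (0.1378/0.18 + 0.1002/0.12)/2 = 0.555. An imbalance of 0.067 SD therefore shifts the RR by about 4%, and one at the 95% limit by a factor of 1.08. The crude intervals extend by a factor of 1.38 to 1.72 on each side.

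**Simulation check.** Five scenarios of 2,000 trials each (ORs 1.5 to 3.0) gave a crude RR that was essentially unbiased, with 95% intervals covering 94.5-96.1%. The SE reduction from adjustment was 0.7% at OR 1.5, 1.2-3.6% at OR 2.0 and 7.7% at OR 3.0, in line with the formula apart from simulation error.

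**The case against.** The strongest reply is that nothing is wrong. Under 1:1 randomization the crude relative risk is a valid estimate, it is transparent, and its interval covers chance imbalance. That stands. A reader might infer that the crude estimates are biased or that imbalance is an uncontrolled error; neither the design nor the coverage check supports this.

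A reader might also infer a loss of power. No test is planned for these incidences: they get a relative risk and an interval, and Protocol 9.5.3 rules out inferential analysis of the safety data.

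Nor is baseline SBP wholly ignored. SAP 2.2.1 shows the events of special interest, which under SAP 2.8.1.4 include hyperkalemia and symptomatic hypotension, by SBP at randomization and by baseline eGFR. A subgroup display gives no adjusted overall estimate, though, and potassium has no subgroup.

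It is tempting, too, to say that baseline potassium comes from the same assay that defines the event. No section says so, and Protocol 6.5.5 allows local tests at unscheduled visits.

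Two further points stand. The prognostic link may be weak, because eligibility truncates both baselines and SBP sets the starting dose. And an adjusted model that drops patients with no baseline value could lose what it gains: at OR 1.5 the variance gain is only about 1-2%, which losing 1-2% of patients would cancel.

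**Conclusion.** The point holds as a minor one. Both documents leave collected and plausibly prognostic baselines out of the relative risks for symptomatic hypotension and hyperkalemia. The cost is a modest loss of precision, under 3% of log-scale interval width up to OR 2.0 per SD and about 3-6% at 2.7, plus the loss of protection against conditional imbalance. Validity is not in question, and in the worked examples the interval moves only in the second decimal place at OR 2.0.

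The size rests on an assumed prognostic strength, on borrowed event rates and on a single covariate. The two-covariate model suggested for hyperkalemia was not calculated. The case for acting is that the change is almost free, targets the same marginal relative risk, and is credible only if specified before unblinding.

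**What to change.** In SAP 2.7.2, keep the crude counts, percentages and relative risks. Beside them, pre-specify a marginally standardized relative risk with 95% CI (delta method or bootstrap) on the same analysis set:

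- **Symptomatic hypotension:** logistic model with arm and baseline SBP.
- **Hyperkalemia:** logistic model with arm, baseline potassium and baseline eGFR. State the 95% CI explicitly, since SAP 2.7.2 spells it out only for symptomatic hypotension.
- **Missing baseline:** keep the patient in the model by a simple stated rule, for example the Visit 1 value or else the overall mean, set without regard to arm.
- **Angioedema:** leave unadjusted. At rates like the 0.5% and 0.2% quoted in Protocol 1.1, 441 per arm would give about 2 and 1 events (441 × 0.005 = 2.2; 441 × 0.002 = 0.9).

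The cost is a few lines of SAP text and code, with no new data and no change to the marginal relative risk being estimated.

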9.5.3 Other safety variables

The safety and tolerability assessments are listed below:

- AEs and SAEs
- Sitting systolic, diastolic BP, and pulse pressure
- Heart rate
- Laboratory values

The assessment of safety will be based primarily on the frequency of adverse events, SAEs, and laboratory abnormalities. Other safety data will be summarized as appropriate.

The incidence of treatment-emergent adverse events (new or worsened) will be summarized by primary system organ class, preferred term, severity, and relationship to study drug. In addition, the incidence of death, SAEs, and AEs leading to discontinuation will be summarized separately by primary system organ class and preferred term.

Laboratory data will be summarized by presenting shift tables using extended reference ranges (baseline to most extreme post-baseline value), by presenting summary statistics of raw data and change from baseline values (mean, median, standard deviation, 25th and 75th percentiles, interquartile range, minimum and maximum) and by the flagging of notable values in data listings.

Data from other tests (e.g., ECG or vital signs) will be listed, notable values will be flagged, and any other information collected will be listed as appropriate.

Safety analyses will be performed based on the Safety Set. There will be no inferential analyses of the safety data.

9.5.5 Pharmacokinetics

Not Applicable.

